4.2 Inclusion and Exclusion Criteria

All individuals must meet all of the inclusion criteria in order to be eligible to participate in the study:

1. The subject is between the ages of 30 and 75 years.
2. Subject is planning to undergo arthroscopic surgery for full-thickness rotator cuff tear (RCT)
3. Two tendon tears or tear size equal to or greater than 3 cm in either the AP or ML dimension
4. Primary rotator cuff repair
5. Stage II fatty infiltration or higher of the supraspinatus or infraspinatus muscle based on preoperative MRI

6. Subject has a dual x-ray absorptiometry (DXA) or anterior posterior x-ray view of the target shoulder

All individuals meeting any of the exclusion criteria will be excluded from study participation:

1. The subject is unable or unwilling to sign the patient informed consent, approved by the Institutional Review Board.
2. The subject objects to the use of allograft
3. Grade 1 or lower fatty infiltration of the supraspinatus AND infraspinatus muscle
4. Complete full-thickness subscapularis tears of greater than the superior one third of the tendon (Lafosse grade 3 and above)
5. Less than 2 mm joint space of the glenohumeral joint on either an anteroposterior or axillary radiograph
6. Recurrent shoulder instability
7. Corticosteroid injection in the operative shoulder within one month of surgery
8. Revision rotator cuff repair
9. Subject preoperative MRI taken more than 12 months prior to surgery
10. Pregnant or planning to become pregnant during the study period
11. Workman's compensation case
12. Subject has conditions or circumstances that would interfere with study requirements.

All individuals who meet any of the intraoperative exclusion criteria will also be excluded from study participation:

1. Partial rotator cuff repairs
2. Lafosse grade 3 or higher subscapularis tears

4.3 Discontinuation of Subjects

Subject Screen Failure

Subject that leaves the study for any reason prior to the surgical visit will be considered a screen failure. Screen failures are not included in the subject total and will be replaced.

Subject and Investigator Withdrawal

Subjects will be informed that they have the right to withdraw from the study at any time for any reason, without prejudice to their medical care. The Investigator(s) may elect at any time to withdraw a subject from the study for any reason. Subjects who are withdrawn for any reason from the study after treatment will not be replaced. Subjects who withdraw consent and refuse to complete the follow-up assessment will be considered off-study at that time.

Lost to Follow-up

If the Investigator(s) reports a subject as lost to follow-up, the site will ensure that documentation is complete regarding the reason(s) this has occurred and will ensure that every attempt is made by the Investigator(s) to contact the subject or significant other persons associated with the subject to determine subject status. Appropriate documentation will consist of at least two documented attempts at contact via telephone by the site.

The primary reason for termination or discontinuation of any subject will be documented in the EDC.

4.4 Randomization Procedures

Randomization shall be performed during surgery after intra-operative inclusion/exclusion eligibility has been met, using computer-generated randomization. Patients will be randomized to have either the addition of DAA following a standard rotator cuff repair (DAA Group) or standard Rotator Cuff repair without DAA (Control group).

Intra-operative exclusion criteria:

1. Partial rotator cuff repairs
2. Lafosse grade 3 or higher subscapularis tears

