8.3	Anticipated Adverse Events	Error! Bookmark not defined.
8.4	Adverse Event Documentation.....	25
9	STATISTICAL CONSIDERATIONS.....	26
9.1	Sample Size	26
9.2	Descriptive Statistics.....	27
9.3	Handling of Missing Data	27
9.4	Demographics and Baseline Characteristics	27
9.5	Analysis of Study Outcomes	27
	9.5.1 Primary Outcomes.....	27
	9.5.2 Secondary Outcomes.....	28
	9.5.3 Objective Outcomes	28
10	ETHICS/PROTECTION OF HUMAN SUBJECTS.....	28
10.1	Ethical Standards and Guidelines	28
10.2	Institutional Review Board/ Ethics Committee	28
10.3	Informed Consent Process	29
10.4	Subject Confidentiality	29
11	DATA HANDLING AND RECORD KEEPING	30
11.1	Data Management Responsibilities	30
11.2	Data Capture Methods.....	30
11.3	Study Records Retention	30
11.4	Protocol Deviations.....	31
11.5	Amendments to the Protocol.....	31
12	STUDY CLOSE OUT	31
13	PUBLICATION/DATA SHARING POLICY	31
14	BIBLIOGRAPHY.....	32
	SUPPLEMENTAL MATERIALS	33
	APPENDICES.....	33

PROTOCOL SUMMARY

Title:	A Randomized, Post-market Study Evaluating Dermal Allograft Augmentation of Large and Massive Rotator Cuff Tears
Summary:	The purpose of this study is to compare postoperative healing of large and massive rotator cuff tears with preoperative MRI confirmed fatty infiltration stage II and higher repaired with or without dermal allograft augmentation (DAA).
Objectives and Outcome Measures:	
The primary objective is to evaluate postoperative healing of rotator cuff repair with and without DAA.
 
Primary: The primary outcome measure is healing evaluation in MRI
 
• MRI Post-Operative Assessment (Goutallier Stage and Sugaya Classification) 
Secondary: The secondary outcome measures are patient-reported outcome measures from validated outcome scoring systems, including:
 
• American Shoulder and Elbow Surgeons Score (ASES)• Single Assessment Numeric Evaluation score (SANE)• Visual Analog Scale (VAS) for pain• Veterans RAND Health Survey (VR-12)
Population:	Males and females between the ages of 30 and 75 years that require surgery for large and massive rotator cuff tears
Phase:	Post market
Description of Treatment:	Rotator cuff repair with or without augmentation using decellularized human dermal allograft.

Inclusion and Exclusion Criteria

Inclusion criteria:

1. The subject is between the ages of 30 and 75 years.
2. Subject is planning to undergo arthroscopic surgery for full-thickness rotator cuff tear (RCT)

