3 STUDY DESIGN

3.1 Study Design and Rationale

This is a prospective randomized study comparing the outcomes of patients undergoing rotator cuff repair with dermal allograft augmentation (DAA) or a control group without dermal allograft. Patient outcomes will be collected and compared between the two cohorts at two years postoperative and will include a range of subjective and functional outcomes and radiographic imaging. All patients undergoing primary rotator cuff repair surgery will be invited to be part of the study after pre-operative inclusion/exclusion criteria have been met.

Hypothesis: Patients undergoing rotator cuff repair surgery will experience improved tendon healing with the use of CuffMend™ dermal allograft augmentation.

The purpose of this study is to compare postoperative healing of large and massive rotator cuff tears with preoperative MRI confirmed fatty infiltration stage II and higher repaired with or without dermal allograft augmentation (DAA).

The outcome measures were selected based on the recommendations of the American Academy of Orthopaedic Surgeons (AAOS) and literature review.

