3.3 Study Objectives and Outcome Measures

3.3.1 Study Objectives

The purpose of this study is to compare postoperative healing of large and massive rotator cuff tears with preoperative fatty infiltration stage II and higher repaired with or without DAA.

Primary Hypothesis: Improved postoperative healing with the addition of CuffMend™ DAA, assessed with MRI Imaging

Secondary Hypothesis: Improved Patient-Reported Outcomes and range of motion with the addition of CuffMend™ DAA

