3.5 Subjective Outcome Measures

The subjective data will be collected as listed in the table: The American Shoulder and Elbow Surgeons Shoulder Score, (ASES score), Veterans RAND Health Survey (VR-12), Single Assessment Numerical Evaluation (SANE), and the Visual Analogue Scale (VAS pain) surveys.

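### The patient-reported secondary scores are open to expectation effects, because the available text does not keep patients unaware of an allocation made during surgery

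*Combined protocol and SAP*

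**What the plan says.** All references are to the combined protocol and SAP.

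- **Design.** Section 3.1: "This is a prospective randomized study comparing the outcomes of patients undergoing rotator cuff repair with dermal allograft augmentation (DAA) or a control group". The study is not described there as blinded or as open-label.
- **Allocation.** Section 4.4: "Randomization shall be performed during surgery after intra-operative inclusion/exclusion eligibility has been met". The allocation is generated by computer. The arms are standard repair with or without the dermal allograft (DAA). The section does not say what the patient is told afterwards.
- **Secondary hypothesis.** Section 3.3.1: "Improved Patient-Reported Outcomes and range of motion with the addition of CuffMend™ DAA".
- **Secondary outcomes.** The Protocol Summary says "The secondary outcome measures are patient-reported outcome measures from validated outcome scoring systems, including" and lists ASES, SANE, VAS pain and VR-12. Section 9.5.2 analyses the same four. Section 3.4 adds range of motion, which Section 3.6 assigns to the lead investigator or site research staff.
- **Collection.** Section 3.5, headed as subjective measures: "The subjective data will be collected as listed in the table". The Section 6 schedule has VAS from 2 weeks and all four scores at 26 weeks, 1 year and 2 years. Section 11.2 lets subjects enter questionnaires into the EDC themselves.
- **Analysis.** Section 9.5.2 summarises these scores descriptively by group and permits, but does not require, two-sample t-tests on the changes.
- **Eligibility.** Section 4.2 excludes a patient if "The subject objects to the use of allograft".

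**The concern.** For these four scores the patient is the rater. Every enrolled patient knows that a graft is possible, and the trial hypothesises that it helps. A patient who learns the arm may rate pain or function differently for that reason alone. Under the plan as written, one site may tell patients their arm before the 2-week VAS and another may not, and both would be following the protocol.

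The surgeon cannot be kept unaware of the arm, but the patient plausibly can. Allocation is made in the operating room, the graft goes in through a portal (Section 5.2), and the same section gives one postoperative schedule without distinguishing the arms. The available text neither uses this opportunity nor explains why it is not used.

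At stake is how the patient-reported part of the secondary hypothesis can be read. A difference favouring the graft on pain or function could be a graft effect, an expectation effect or both, and nothing in the planned analysis distinguishes them.

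**Working it through.** **Step 1: is there a masking provision?** The sections where one would be expected, set side by side:

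| Section | What it covers | Patient masking or disclosure rule |
|---|---|---|
| 3.1 | Design label | None stated |
| 3.5, 3.6 | Who provides or measures outcomes | None stated |
| 4.4 | Randomization | Timing and method only |
| 6 | Schedule | No item on perceived allocation |
| 9.5.2 | Secondary analysis | None stated |
| 10.3 | Consent process | Nothing on telling the subject the arm |

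Not available for this check were some front pages, including what follows the heading for the study schematic, and the consent form template (Appendix 2). Absence is shown only for the text that could be read.

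**Step 2: the plan's own sample size.** Section 9.1 assumes healing of 75% against 40%, one-sided alpha 0.025 and 90% power. With the pooled-variance formula and mean proportion 0.575:

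n = [1.960 × √(2 × 0.575 × 0.425) + 1.282 × √(0.75 × 0.25 + 0.40 × 0.60)]² / 0.35² = 39.8, rounded up to 40 per group.

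Allowing for 33% dropout, 40 / 0.67 = 59.7, rounded up to 60 per group. Both figures reproduce. They concern the MRI outcome and would not change with patient masking. They are used here only as the range of patients per arm who might supply scores.

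**Step 3: illustration of an expectation shift.** Assumptions that are not in the documents:

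- the graft has no true effect on the score;
- knowledge of the arm moves the between-group mean by d standard deviations, with d = 0.2, 0.3 or 0.4;
- the optional t-test is read at the upper 2.5% tail.

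The test statistic then follows a noncentral t distribution with 2n − 2 degrees of freedom and noncentrality d × √(n/2). The critical value is 1.991 for n = 40 (78 degrees of freedom) and 1.980 for n = 60 (118 degrees of freedom).

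| d (assumed) | Noncentrality, n = 40 | Favours graft, n = 40 | Noncentrality, n = 60 | Favours graft, n = 60 |
|---|---|---|---|---|
| 0 | 0 | 2.5% | 0 | 2.5% |
| 0.2 | 0.2 × √20 = 0.894 | 14.1% | 0.2 × √30 = 1.095 | 19.1% |
| 0.3 | 1.342 | 26.3% | 1.643 | 37.1% |
| 0.4 | 1.789 | 42.3% | 2.191 | 58.4% |

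A normal approximation gives nearly the same: 14.3%, 26.8% and 43.2% at 40 per arm, and 19.4%, 37.6% and 59.1% at 60 per arm. The 60-per-arm columns assume no loss to follow-up. The same d is applied whatever the visit, although expectation may fade over two years.

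**The case against.** The case on the other side has several parts.

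- **Range of motion is also secondary.** Section 3.4 lists it, and site staff measure it. A reader might infer that every secondary outcome is patient-rated, or that the whole secondary hypothesis is unanswerable. The documents do not support either: the point reaches only the patient-reported part. This objection stands.
- **The primary outcome is untouched.** Healing is judged on MRI and sized on MRI. Who reads the images is a separate question. This stands and limits the weight of the point.
- **The t-test is optional and no secondary alpha is set.** The only success threshold, in Section 9.5.1, is for healing. The percentages above are therefore not error rates of this plan. This stands, but a descriptive difference between groups carries the same possible bias.
- **The shift is assumed.** The documents give no value, so the table shows only what follows if a shift of that size exists. This stands.
- **Differential dropout.** A reader might infer that disappointed controls will leave more often. Section 9.1 allows for up to 33% loss, but nothing ties loss to knowing the arm, so this is not relied on.
- **Masking may leak.** The operating surgeon knows the arm, staff see patients at follow-up, and patients may read operative or MRI reports. Masking would be imperfect, but this does not justify leaving disclosure to each site.
- **A late guess of allocation is contaminated by outcome.** Patients who do well may guess graft. This is right, and it is a reason to ask early as well as late.
- **The unseen pages may contain a rule.** That is possible. If so, Section 4.4 should still state it.

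**Conclusion.** The point holds in limited form. A graft benefit is hypothesised on four scores that patients rate themselves, and the available text does not keep patients unaware of their arm. A between-group difference in those scores or in pain could therefore partly reflect expectation. Agreement with MRI healing or range of motion would be indirect support only.

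The size is unknown. Under the assumed shifts of 0.2 to 0.4 SD, no graft effect and a one-sided 0.025 reading, the illustrative chance of a result favouring the graft is about 14% to 42% at 40 per arm and 19% to 58% at 60 per arm, against 2.5% with no shift.

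The documents do not show that patients will be told their arm, only that nothing available prevents it. The change is worth making because it is cheap and allocation during surgery makes it plausible. It is not a threat to the trial's main result.

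**What to change.** 1. Add to Section 4.4 that site staff will not disclose the assigned arm to the subject until the 2-year surveys are complete, unless disclosure is needed for care or the subject insists. Record each disclosure and its date.
2. Check the consent form and bring it into line with that rule.
3. Ask subjects which treatment they believe they received, first with the 2-week survey, before outcome can drive the guess, and again at 2 years.
4. In Section 9.5.2, state that the patient-reported scores will be presented together with the extent of unmasking: recorded disclosures and perceived allocation by arm.
5. If masking is judged infeasible, declare the study open-label to patients and limit conclusions on patient-reported outcomes and pain accordingly.

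The cost is protocol and consent wording, a disclosure log entry and one survey item at two existing time points. There are no added visits, staff or procedures, and the sample size does not change. The downside is that masking will be imperfect, because patients may see operative or MRI reports and the exception for insistent subjects allows some unmasking. The recorded disclosures and the perceived-allocation item would help to show how far this went.

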4.5 Premature Termination or Suspension of Study

For any study that is prematurely terminated or suspended by the site principal investigator (PI), the PI will promptly inform the IRB/EC and Arthrex and provide the reason(s) for the termination or suspension. Arthrex reserves the right to terminate the study or a site's participation for any reason with written notification as specified in the clinical trial agreement.

5 TREATMENT AND PROCEDURES

5.1 Concomitant Treatments

There are no restrictions on medications or treatments in the study.

5.2 Study Procedures

The surgery is performed as standard of care. Surgeons are advised to review the product-specific surgical technique prior to performing any surgery. Arthrex provides detailed surgical techniques in electronic formats on the Arthrex website.

The rotator cuff will be repaired per each surgeon's preferred method, documenting the number of anchors and usage of single-row or double-row repair.

[figure not shown]
Tears with sufficient mobility to cover the greater tuberosity will be repaired with a knotless double-row technique with a minimum of 4 anchors (SpeedBridge™; Arthrex, Inc.)

In the study group, DAA will be performed with a 1 mm acellular dermal allograft (CuffMend™ graft; Arthrex Inc., Naples, FL) (Figure 1). The DAA is designed to augment the rotator cuff repair. The DAA will be inserted through a portal with a graft spreader. The graft is then secured into the medial rotator cuff tissue. The graft spreader is removed. Finally, the graft is secured into the lateral greater tuberosity with two knotless anchors (3.5 mm PushLock®; Arthrex, Inc.)

Medial graft fixation will be performed with FiberStitch™ RC (Arthrex Inc.) based on surgeon preference. In the FiberStitch™ technique a minimum of two anchors will be used to secure the allograft to the medial tissue. Tears with limited tendon mobility in which only a single-row repair can be performed will be repaired with a knotless technique using inverted mattress FiberTape sutures (Arthrex, Inc) and a medial looped suture (Knotless Ripstop; Arthrex Inc.)

Postoperatively the patient will be placed in a sling for six weeks with hand, elbow, and wrist range of motion only. At six weeks, the sling will be removed, and passive range of motion will be initiated. At nine weeks, active motion will be initiated. At 12 weeks, postoperative strengthening will be allowed. Full activities will be permitted at six months postoperative.

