2 BACKGROUND AND DEVICE DESCRIPTION

2.1 Background Information

Increasing tear size, increasing retraction, and fatty infiltration are the primary factors associated with decreased rates of tendon healing.^{1,2} The retear rate, for example, increases by 4-fold when tear size increases from 1 to 3 cm.² It is well-established that the most common mode of failure in large and massive rotator cuff tears, especially those with fatty degeneration infiltration, is tendon tearing through suture.³ Given the association between tendon healing and functional outcome⁴, it is important to identify techniques that can improve tendon healing.^{5,6,7}

Dermal allograft augmentation (DAA) has been shown to improve the biomechanics of rotator cuff repair, and case reports have described the capability for vascularization and neotendon formation.^{8,9} One study of 42 patients suggested that DAA can improve healing. However, repairs were limited to single-row constructs, which may have lower healing than double-row constructs.

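### Section 4.4 does not require the base repair to be finished before the arm is revealed, and section 5.2 may leave the surgeon some choice of construct at that point

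*Combined protocol and SAP*

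**What the plan says.** Section 5.2 (Study Procedures) describes the base repair in three statements:

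- General: "The rotator cuff will be repaired per each surgeon's preferred method", with the number of anchors and the row type to be documented.
- Mobile tears: "Tears with sufficient mobility to cover the greater tuberosity will be repaired with a knotless double-row technique with a minimum of 4 anchors".
- Tears with limited mobility: "Tears with limited tendon mobility in which only a single-row repair can be performed will be repaired with a knotless technique".

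Section 4.4 (Randomization Procedures) gives the timing: "Randomization shall be performed during surgery after intra-operative inclusion/exclusion eligibility has been met, using computer-generated randomization". The intra-operative exclusions listed there are partial repairs and subscapularis tears of Lafosse grade 3 or higher. The experimental arm is described in these words: "Patients will be randomized to have either the addition of DAA following a standard rotator cuff repair".

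Section 2.1 comments on an earlier study of DAA that its "repairs were limited to single-row constructs, which may have lower healing than double-row constructs".

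The schedule in section 6 places the randomization form and the surgical details form in the same surgery column and gives no order between them. Section 4.4 states no stratification by construct. Section 9.5.1 plans a chi-square test with no adjustment for construct.

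**The concern.** Randomisation makes the arms comparable in everything settled before the arm is known. If part of the base repair is settled afterwards, by a surgeon who knows whether a graft will follow, the arms can differ in construct as well as in graft. The primary comparison of healing on MRI would then mix the two effects.

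Three features of the text leave this route open. Section 4.4 makes eligibility, not completion of the repair, the condition for randomising. Section 5.2 can be read as leaving row type and anchor number partly to preference. Section 2.1 itself links row type to healing. Adjusting for construct in the analysis would not reliably restore the comparison, because a construct chosen after allocation is a consequence of the arm and not a baseline factor.

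**Working it through.** **The plan's own figure.** Section 9.1 assumes healing of 75% (treatment) and 40% (control), one-sided alpha 0.025 and 90% power. With the pooled Z-test, the mean proportion is 0.575 and

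n = [1.960 × √(2 × 0.575 × 0.425) + 1.2816 × √(0.75 × 0.25 + 0.40 × 0.60)]² / 0.35² = (1.370 + 0.838)² / 0.1225 = 39.8, so 40 per group.

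Allowing for dropout, 40 / (1 − 0.33) = 59.7, so 60 per group. Both figures reproduce, and nothing in this point disputes them.

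**The texts side by side.**

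1. *What must precede randomisation?* Section 4.4 requires that the two intra-operative exclusions have been ruled out. No sentence requires the repair to be complete, or its construct chosen and recorded.
2. *What is still open then?* If the preference sentence in section 5.2 governs, row type and anchor number may be open. If the mobility statements govern, row type follows from a judgement of mobility made during surgery. Anchor number in mobile tears then has a minimum but no fixed value.
3. *Who knows the arm?* The operating surgeon has to know it in order to place the graft or omit it.
4. *Does construct matter for the endpoint?* Section 2.1 says that it may, without giving a rate.

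**Illustration of size.** All inputs other than the 40% control rate and the 40 per group are assumptions.

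Bias = (difference between arms in share of double-row repairs) × (difference in healing rate between double-row and single-row).

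- 10 points × 10 points: 0.10 × 0.10 = 1 point
- 20 points × 20 points: 0.20 × 0.20 = 4 points
- 20 points × 30 points: 0.20 × 0.30 = 6 points

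For each bias b, the rejection probability of the one-sided pooled Z-test at 0.025 is summed exactly over the two binomial distributions. False success uses 0.40 + b against 0.40, with no graft effect. Power uses 0.75 + b against 0.40.

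| Bias, 40 per arm | False success | Power |
|---|---|---|
| none | 2.6% | 90.7% |
| 1 point for DAA | 3.2% | – |
| 4 points for DAA | 5.9% | – |
| 6 points for DAA | 8.3% | – |
| 4 points against DAA | 1.0% | 82.3% |
| 6 points against DAA | 0.6% | 76.8% |

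The unbiased value is 2.6% rather than 2.5% because the binomial counts are discrete. If all 60 per arm were evaluable, 4 and 6 points for DAA would give 6.7% and 10.1%: a larger sample does not dilute a bias of this kind.

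**The case against.** The strongest reply is that the intended sequence is already repair, then randomise, then graft. Section 4.4 describes the graft as added following a standard repair, and whether a repair is partial is most naturally judged once it has been done. This is a plausible reading and may be what the sponsor means. But the phrase about the graft orders the surgical steps and does not time the allocation, and the partial-repair criterion can also be met by judging that a full repair is feasible. The sequence is plausible but unstated.

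Second, section 5.2 can be read as a general sentence followed by specific rules, with row type then following from tendon mobility. This largely stands. The statements still need reconciling, but they apply alike to both arms, and variation in repair common to both arms does not bias a randomised comparison. A reader might infer that the wording of section 5.2 biases the trial by itself. It does not; it matters only together with the open timing in section 4.4.

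Third, a reader might infer that a surgeon could declare a repair partial differently by arm. As written, section 4.4 applies that exclusion before randomisation. It is exposed only in the narrower case where a full repair is judged feasible, the patient is randomised, and the repair then proves partial.

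Fourth, the numbers are assumed and the bias could run either way. A surgeon might, for instance, reinforce the repair that will receive no graft. This stands, and is why both directions are shown. Even the largest bias illustrated, 6 points, is small beside the planned 35-point difference.

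**Conclusion.** The point holds as a gap in the stated order of events. The plan does not require the base repair to be complete and recorded before the arm is revealed, and section 5.2 is loose enough that some choice of construct may remain at that moment. The protocol itself regards row type as possibly related to healing.

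The documents do not support saying that the arm will influence the repair, or that the result will favour DAA. They contain no evidence on surgeons' behaviour by arm and no healing rate by construct. The illustrated range runs from near-negligible (a 1-point bias moves false success from 2.6% to 3.2%) to material in either direction: false success up to 8.3%, or power down to 76.8%, at 40 per arm with a 6-point bias. It rests on the assumed imbalances and construct differences above, with control healing at 40%.

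The change is worth making because it closes the route at little cost, not because bias has been shown.

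**What to change.** 1. In section 4.4, state that the allocation is opened only after the base repair is complete and its row type, anchor number and completeness have been recorded. This also settles the narrower partial-repair case, because completeness is then known before randomisation.
2. In section 5.2, reconcile the surgeon-preference sentence with the mobility statements so that one rule for the base repair applies to both arms. Which rule is for the sponsor and investigators to decide.

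The cost is protocol wording, a short recording step in theatre before allocation, and slightly later graft preparation in DAA cases. The recording step is new, because the schedule sets no order between the randomization and surgical details forms. The sample size does not change. With construct recorded before allocation, it could also serve as a pre-specified covariate or stratification factor, but the fix does not depend on that.
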